7.5. Toxicity Management

7.5.1. Observation for Drug-Induced Liver Injury

At baseline, some subjects may have liver biochemistry levels above the ULN. Baseline values for liver tests **CCI** will be determined by averaging the values obtained between and including screening and Day 1. Please refer to the Covance Laboratory Manual or individual subject Covance laboratory report for gender and age specific reference ranges.

On-treatment elevations **CCI** should be confirmed with repeat testing within 48-72 hours of results. If the results are confirmed, and if no other cause of the laboratory abnormalities is immediately apparent, notify the medical monitor. Subjects with **CCI** elevations as per [Figure 7-1](#) must be placed into close observation (as described below).

Figure 7-1. On-Treatment CCI Monitoring Requiring Close Observation

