7.5.2. Close Observation

[figure not shown]
Close observation includes:

- Repeating liver biochemistries (CCI [REDACTED]) and obtaining a CPK level within 48-72 hours of confirmatory results collected prior to entering close observation.
- Obtaining a more detailed history of symptoms and prior or concurrent disease
- Obtaining a history of CM use (including nonprescription medications and herbal and dietary supplement preparations), alcohol use, recreational drug use, and special diets
- Obtaining a history of exposure to environmental chemical agents
- Ruling out other causes of liver disease as needed (obtain viral hepatitis panel, imaging for evaluation of biliary tract disease, etc. if required in the opinion of the investigator)
- Continue to monitor liver biochemistries at least twice weekly. Frequency can decrease to once a week or less if abnormalities stabilize or study drugs have been discontinued and the subject is asymptomatic.

During a period of close observation for DILI, study drugs can be continued, if desired, at the discretion of both the medical monitor and investigator.

If on-treatment elevations of ALT and/or AST exceed the values shown in [Figure 7-2](#), are confirmed on repeat testing within 48-72 hours of results, and no alternative cause is immediately apparent, the subject must be placed into close observation and study drug must be withheld.

Figure 7-2. On-Treatment Monitoring Requiring Withholding of Study Drugs

* Unless subject has Gilbert's syndrome, in which case a direct bilirubin > 2 x baseline (average of Screening & Day 1 values) will be used instead of total bilirubin.
**If not on therapeutic anticoagulation (e.g. warfarin). If on therapeutic anticoagulation, INR criteria is disregarded.

Abbreviations:

ULN – Upper limit of normal range
TB – Total Bilirubin

If study drugs are withheld, they may be reintroduced with approval from the Gilead medical monitor. In instances where study drug is withheld in the context of DILI, up to a 4-week study drug dose interruption is permitted. Upon resuming study drug, the subject should restart at prior dose as outlined in [Section 3](#).

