3.7.2. Analysis Visit Windows

Subject visits might not occur on protocol-specified days. Therefore, for the purpose of analysis, observations will be assigned to analysis windows.

On-treatment visit windows will be calculated from study Day 1 or the first post-interruption study drug dosing date for selected efficacy measures, elastography, and safety laboratory data.

Selected safety and efficacy data, unless otherwise specified, collected up to and including the last dosing date + 30 days, will be mapped according to the following analysis windows unless the nominal visit name is early termination (ET) or Follow-Up.

The analysis windows for selected measures are provided in [Table 3-1](#) to [Table 3-3](#). The algorithm for assigning baseline analysis window does not apply to the liver tests (ALP, total bilirubin, ALT, AST, and GGT). For these 5 parameters, the baseline values will be determined by averaging the values obtained at Screening and Baseline/Day 1, and no specific study day is associated with the average values.

Table 3-1. Analysis Visit Windows for Chemistry, eGFR, Hematology, Coagulation, Child-Pugh (CP)/ Model for End-stage Liver Disease (MELD) Scores, Pruritus VAS, 5D-Itch and Biomarkers, Including hsCRP, ELF™ Score and Components, FibroSURE/FibroTest® and Selected Components, Bile Acids, FGF19, C4.

Nominal Visit	Nominal Study Day/Post-interruption Study Day	Visit Window Study Day/Post-interruption Study Day	
		Lower Limit	Upper Limit
Baseline/Post-interruption Day 1	1	(none)	1
Week 1/Post-interruption Week 1	8	2	18
Week 4/Post-interruption Week 4	29	19	42
Week 8/Post-interruption Week 8	57	43	70
Week 12/Post-interruption Week 12	85	71	≥85

Table 3-2. Analysis Visit Windows for IBD Symptoms

Nominal Visit	Nominal Study Day/Post-interruption Study Day	Visit Window Study Day/Post-interruption Study Day	
		Lower Limit	Upper Limit
Baseline/Post-interruption Day 1	1	(none)	1
Week 4/Post-interruption Week 4	29	2	42
Week 8/Post-interruption Week 8	57	43	70
Week 12/Post-interruption Week 12	85	71	≥85

Table 3-3. Analysis Visit Windows for QoL Questionnaires and FibroScan

Nominal Visit	Nominal Study Day/Post-interruption Study Day	Visit Window Study Day/Post-interruption Study Day	
		Lower Limit	Upper Limit
Baseline/Post-interruption Day 1	1	(none)	1
Week 12/Post-interruption Week 12	85	2	≥ 85

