7.2.3. Liver-related Laboratory Evaluations

Liver-related abnormalities after initial study drug dosing will be examined and summarized using the number and percentage of subjects who were reported to have the following laboratory test values for postbaseline measurements.

For subjects with normal baseline ALT/AST (\leq ULN):

- Subjects meeting criteria for close observation
 - ALT/AST $> 3 \times$ ULN
- Subjects meeting any one of the following criteria for withholding study drug
 - ALT/AST $> 8 \times$ ULN
 - ALT/AST $> 5 \times$ ULN for 2 weeks
 - ALT/AST $> 3 \times$ ULN and total bilirubin $> 2 \times$ ULN (or direct bilirubin $> 2 \times$ baseline in subjects with Gilbert's syndrome)
 - ALT/AST $> 3 \times$ ULN and INR > 1.5 (if not on anticoagulation)

For subjects with elevated baseline ALT/AST ($>$ ULN)

- Subjects meeting criteria for close observation
 - ALT/AST $> 2 \times$ Baseline or > 300 U/L
- Subjects meeting any one of the following criteria for withholding study drug
 - ALT/AST $> 8 \times$ Baseline or > 500 U/L
 - ALT/AST $> 3 \times$ Baseline or > 300 U/L, and total bilirubin $> 2 \times$ ULN (or direct bilirubin $> 2 \times$ Baseline in subjects with Gilbert's syndrome)
 - ALT/AST $> 3 \times$ Baseline or > 300 U/L, and INR > 1.5 (if not on anticoagulation)

The summary will include data from all postbaseline visits up to 30 days after the last dose of study drug. For individual laboratory tests, subjects will be counted once based on the most severe postbaseline values. For both the composite endpoint of AST or ALT and total bilirubin, subjects will be counted once when the criteria are met at the same postbaseline visit date. The denominator is the number of subjects in the Safety Analysis Set who have nonmissing postbaseline values of all relevant tests at the same postbaseline visit date. A listing of subjects who met at least 1 of the above criteria will be provided.

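### SAP 7.2.3 labels unconfirmed liver-test values as meeting the protocol's close-observation and withholding criteria, and direct bilirubin is missing from the averaged baselines (minor)

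*SAP*

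**What the plan says.** **Protocol.** Section 7.5.1 says that on-treatment elevations "should be confirmed with repeat testing within 48-72 hours of results". The first bullet of 7.5.2 places the confirmatory result before entry to close observation. Section 7.5.2 then requires drug to be withheld when ALT/AST elevations exceed the Figure 7-2 values, "are confirmed on repeat testing within 48-72 hours of results, and no alternative cause is immediately apparent". The footnote to Figure 7-2 replaces total bilirubin in Gilbert's syndrome with "direct bilirubin > 2 x baseline (average of Screening & Day 1 values".

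**SAP.** Section 7.2.3 reports subjects meeting criteria for close observation and "Subjects meeting any one of the following criteria for withholding study drug". Its counting rules are "For individual laboratory tests, subjects will be counted once based on the most severe postbaseline values" and, for ALT/AST combined with total bilirubin, "subjects will be counted once when the criteria are met at the same postbaseline visit date". It mentions neither a repeat nor an alternative cause. One criterion, for subjects with normal baseline ALT/AST, does require persistence: above 5 x "ULN for 2 weeks".

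On baselines, SAP 3.7.2 says "The algorithm for assigning baseline analysis window does not apply to the liver tests (ALP, total bilirubin, ALT, AST, and GGT". SAP 3.7.3 averages the same five tests. Direct bilirubin is not among them, so it takes the SAP 3.7.3 default: the last nonmissing value on or before first dose.

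**The concern.** The SAP takes over the protocol's decision labels but not the conditions attached to them. A value that its own repeat refutes still enters the table as meeting the criteria. So does a withholding-level value with an obvious other cause. Dropping a condition can only raise a count.

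Laboratory tests are part of the primary endpoint (protocol 8.1.2). SAP 7.2.1 drops numeric laboratory summaries and SAP 7.4 drops concomitant medications, so this table carries more of the liver-safety message than it otherwise would. Protocol 1.5 reports that most Grade 3 or 4 ALT/AST elevations in the earlier Phase 2 NASH and PSC studies had another explanation, natural fluctuation among them. With about 20 subjects planned and enrollment ended early, each subject moves a percentage by at least 1/20 = 5 points.

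The direct-bilirubin mismatch means that, for a subject with Gilbert's syndrome, the table can apply a different threshold from the one the site applied.

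**Working it through.** The documents give no figure to reproduce. The mismatch is textual, and the arithmetic below only indicates its size.

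**1. Conditions side by side**

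| Condition | Protocol: close observation | Protocol: withholding | SAP 7.2.3 |
|---|---|---|---|
| Repeat at 48-72 h | Yes (7.5.1; 7.5.2 first bullet) | Yes (7.5.2) | No, except the 2-week criterion |
| No apparent other cause | Not attached (in 7.5.1 it governs notifying the medical monitor) | Yes (7.5.2) | No |
| Direct-bilirubin baseline | - | Mean of Screening and Day 1 | Last pre-dose value |

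The content of Figures 7-1 and 7-2 is not available, so numeric thresholds cannot be compared between the documents.

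**2. Single value against confirmed value**

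Inputs:
- ALT 156 U/L, the upper quartile of the 100 mg group in protocol Table 1-1 (noncirrhotic PSC).
- Five post-baseline values: Weeks 1, 4, 8, 12 and follow-up.
- SAP thresholds for elevated baseline: 300 U/L (close observation) and 500 U/L (withholding).
- Assumed: lognormal values with median 156, no drug effect, independent visits, within-subject CV 20-40%.

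Formulas: s = sqrt(ln(1 + CV²)); z = ln(threshold/156)/s; p = P(Z > z); chance of at least one exceedance = 1 - (1 - p)^5.

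| CV | s | z at 300 | p at 300 | At least one > 300 | z at 500 | At least one > 500 |
|---|---|---|---|---|---|---|
| 20% | 0.198 | 3.30 | 0.0005 | 0.2% | 5.88 | about 0 |
| 30% | 0.294 | 2.23 | 0.0130 | 6.3% | 3.97 | 0.02% |
| 40% | 0.385 | 1.70 | 0.0448 | 20.5% | 3.02 | 0.6% |

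In 20 such subjects at CV 30-40%, about 1.3 to 4.1 would be counted for close observation through fluctuation alone (20 x 0.063; 20 x 0.205). Only about 0.004 to 0.12 would be counted for the 500 U/L criterion.

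Requiring an independent repeat above 300 U/L replaces p by p². This gives 1 - (1 - 0.0130²)^5 = 0.08% at CV 30% and 1 - (1 - 0.0448²)^5 = 1.0% at CV 40%. If value and repeat correlate at 0.3-0.8, the figures are about 0.4-2.5% and 3-10%.

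The close-observation criterion also counts values above 2 x baseline. A simulation of 400,000 subjects with this arm, an averaged baseline and independent repeats gave, single against confirmed: 1.0% and 0.03% (CV 20%), 12.6% and 1.2% (CV 30%), 30.7% and 5.1% (CV 40%). The 300 U/L figures alone are therefore on the low side for that row.

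**3. Direct-bilirubin threshold**

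Let S be Screening and D be Day 1, the only two pre-dose values. Protocol threshold: 2 x (S + D)/2 = S + D. SAP threshold: 2D. Ratio of SAP to protocol: 2D/(S + D).

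- S = 0.4, D = 0.2 mg/dL: protocol > 0.6, SAP > 0.4, ratio 0.67.
- S = 0.2, D = 0.4 mg/dL: protocol > 0.6, SAP > 0.8, ratio 1.33.

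The two agree only when S = D. Bilirubin counts only together with an ALT/AST elevation. Assume stable Gilbert's subjects with mean direct bilirubin 0.2-0.8 mg/dL, CV 25-35% and rounding to 0.1, and an independent ALT at 156 U/L with CV 30-40%. Simulated chances of meeting the bilirubin condition with ALT above 300 U/L at the same visit are about 0.1-1.4% with the last value and 0.03-0.8% with the average.

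**The case against.** The strongest reply is that SAP 7.2.3 opens as a descriptive count of subjects with given laboratory values. Worst-value counting is a sensitive and defensible safety display, and protocol 7.5.2 can be read as treating the threshold and its confirmation as separate things. The SAP also promises a listing of subjects meeting any criterion, and SAP 7.2 promises chronological by-subject laboratory listings in which recorded retests can be seen. In a study this small, with no formal testing, a careful reader can work out what happened. All of this stands, and it makes the point minor. It does not justify the label: a listing does not correct a row headed as the protocol's decision criterion.

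A reader might infer more than the documents support:

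- *That the withholding row is badly inflated.* Step 2 shows that fluctuation rarely reaches 500 U/L, and the 2-week criterion already needs persistence.
- *That the reported count is too high by the ratio of single to confirmed chances.* Those are false-positive rates in stable subjects. Genuine sustained elevations would appear in both rows.
- *That the protocol excludes apparent other causes from both actions.* The visible text attaches that condition only to withholding.
- *That the table would create protocol deviations or ought to match the interruption counts.* Under SAP 4.3 deviations are documented during routine monitoring. The interruptions in SAP 4.1 are PI-approved ones, which under protocol 7.5.5 means holds longer than 5 days, so exact agreement was never to be expected.

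One further objection shapes the fix. Reserving the label for confirmed values could hide a subject whose retest was missed.

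**Conclusion.** Both mismatches are in the text. Apart from the 2-week criterion, SAP 7.2.3 can count a subject as meeting a protocol criterion without the confirmation that the protocol requires and, for withholding, without regard to an apparent alternative cause. The effect lies mainly in the close-observation row: about 6-20% of stable subjects at ALT 156 U/L if CV is 30-40%, and about 0-1% at CV 20%. It is small for single-test withholding thresholds. The CVs are assumptions and the ALT level comes from a noncirrhotic population, so these sizes are illustrative.

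The direct-bilirubin baseline also differs between the documents, and the resulting threshold can err in either direction. It matters only for subjects with Gilbert's syndrome who also have raised ALT/AST. A reader might take the chance of exceeding 2 x direct-bilirubin baseline on its own (about 6-20% with the last value, 2-14% with the average) as the size of the problem, but SAP 7.2.3 never counts bilirubin alone.

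Severity: minor. The point concerns labelling and consistency of the analysis, not any clinical rule.

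**What to change.** In SAP 7.2.3:

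- Keep the existing rows but label them *threshold exceeded, any single value (unconfirmed)*. The 2-week criterion can keep its own wording.
- Add a row per criterion for values confirmed on the protocol's 48-72 hour repeat. Show subjects with no repeat separately; do not drop them.
- In the listing, note the alternative cause where it is recorded. No dedicated field is visible in the documents, so this may have to come from existing comments or adverse event records.

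In SAP 3.7.2 and 3.7.3, add direct bilirubin to the tests whose baseline is averaged, to agree with the Figure 7-2 footnote.

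The cost is a few lines of SAP text and one or two extra rows per criterion. No new assessments are needed.

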Laboratory data collected during the study will be analyzed and summarized using both quantitative and qualitative methods. Summaries of laboratory data will be provided for the Safety Analysis Set and will include data collected up to the last dose of study drug plus 30 days. The analysis will be based on values reported in conventional units. When values are BLQ, they will be listed as such, and the closest imputed value will be used for the purpose of calculating summary statistics as specified in Section 3.6. Hemolized test results will not be included in the analysis, but they will be listed in by-subject laboratory listings.

A by-subject listing for laboratory test results will be provided by subject ID number and visit in chronological order for hematology, eGFR, serum chemistry, coagulation, and urinalysis separately. Values falling outside of the relevant reference range and/or having a severity grade of 1 or higher on the Common Toxicity Criteria for Adverse Events (CTCAE) severity grade as described in [Appendix 2](#) will be flagged in the data listings, as appropriate.

No formal statistical testing is planned.

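### The ALT/AST-plus-bilirubin row of the liver table leaves out subjects whose two elevations never overlap on one sampled date, and no time-window count is planned

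*SAP*

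**What the plan says.** SAP 7.2.3 counts subjects who meet close-observation and withholding criteria, separately for normal and elevated baseline ALT/AST. Among the withholding criteria are ALT/AST > 3 x ULN with total bilirubin > 2 x ULN (normal baseline), and ALT/AST > 3 x baseline or > 300 U/L with the same bilirubin limit (elevated baseline). Direct bilirubin is used in Gilbert's syndrome. A parallel pair of criteria uses INR > 1.5 in place of bilirubin.

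For the bilirubin composite, "subjects will be counted once when the criteria are met at the same postbaseline visit date". The denominator is the Safety Analysis Set subjects with "nonmissing postbaseline values of all relevant tests at the same postbaseline visit date". Single tests follow a different rule: "For individual laboratory tests, subjects will be counted once based on the most severe postbaseline values". On the period covered: "The summary will include data from all postbaseline visits up to 30 days after the last dose of study drug".

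Two listings accompany the table. In 7.2.3: "A listing of subjects who met at least 1 of the above criteria will be provided". In SAP 7.2: "A by-subject listing for laboratory test results will be provided by subject ID number and visit in chronological order", with serum chemistry among the panels.

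Protocol 7.5.2 determines what data there will be. If ALT/AST elevations exceed the Figure 7-2 values, "are confirmed on repeat testing within 48-72 hours of results", and have no other apparent cause, the subject enters close observation and drug is withheld. Under close observation the instruction is "Continue to monitor liver biochemistries at least twice weekly", easing to weekly or less once values stabilise, or once drug is stopped and the subject has no symptoms.

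**The concern.** Close observation produces serial liver tests a few days apart. In such a series ALT/AST can fall back below its limit before bilirubin passes its own. A rule that needs both on one date then records no event, although both limits were crossed in the same episode.

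The stricter rule falls only on the composite, since single tests use the worst value at any postbaseline time. Work across dates is not foreign to the table either: one withholding criterion for normal-baseline subjects is ALT/AST > 5 x ULN for 2 weeks.

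The row matters because safety is the primary endpoint, there is no control arm, and the SAP has dropped much of the other safety output: numeric laboratory summaries (7.2.1), vital signs (7.3), concomitant medications (7.4) and ECG (7.5). The liver table is one of the few safety tabulations left. In a study of this size, a composite row reading 0 instead of 1 reads quite differently.

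**Working it through.** The documents give no event rate, lag or sample-size figure on this point, so there is nothing of the plan's to reproduce. The check applies the written rule.

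**1. Direction.** Same-date rule: some date t has ALT/AST above its limit and bilirubin above its limit. Window rule of w days: some date t1 has ALT/AST above its limit, and some date t2 with 0 ≤ t2 − t1 ≤ w has bilirubin above its limit. Taking t1 = t2 shows that anyone meeting the first meets the second. The same-date numerator can equal the windowed numerator but never exceed it.

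**2. Illustrative subjects.** These are invented, with normal baseline and limits of 3 x ULN (ALT) and 2 x ULN (bilirubin).

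| Subject | Day: ALT / bilirubin, x ULN | Same date | 7-day | 14-day | 30-day |
|---|---|---|---|---|---|
| A | 29: 7 / 1.2; 33: 5 / 1.8; 36: 3.6 / 2.3 | counted | counted | counted | counted |
| B | 29: 7 / 1.2; 33: 3.4 / 1.8; 36: 2.6 / 2.3 | not counted | counted | counted | counted |
| C | 29: 7 / 2.4 | counted | counted | counted | counted |
| D | 29: 4 / 1.0; 57: 1 / 2.4 | not counted | not counted | not counted | counted |

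A and B both have bilirubin crossing 7 days after the ALT peak (36 − 29). They differ only in whether ALT is still above 3 x ULN on that day. D crosses 28 days later (57 − 29).

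**3. How long an overlap stays possible.** If ALT falls exponentially, the days above 3 x ULN after the peak are half-life × log2(peak / 3). The half-lives are assumptions.

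| ALT peak, x ULN | 1 day | 2 days | 4 days | 7 days |
|---|---|---|---|---|
| 4 | 0.4 | 0.8 | 1.7 | 2.9 |
| 5 | 0.7 | 1.5 | 2.9 | 5.2 |
| 8 | 1.4 | 2.8 | 5.7 | 9.9 |
| 20 | 2.7 | 5.5 | 10.9 | 19.2 |

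For example, 4 × log2(5 / 3) = 2.9 days. A lag of a few days can fall on either side of the rule.

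**4. Where a missed subject still appears.** The composite's ALT/AST limit is never below the close-observation limit: > 3 x ULN in both for normal baseline; > 3 x baseline or > 300 U/L against > 2 x baseline or > 300 U/L for elevated baseline. B and D are therefore counted in the close-observation row and appear in the 7.2.3 listing. ALT, AST and total and direct bilirubin are one chemistry panel (Protocol 6.8.1), so the bilirubin values are in the chemistry listing. The graded laboratory table gives only part of the picture: with normal baseline, SAP Appendix 2 makes bilirubin > 1.5 to 3.0 x ULN Grade 2. A value between 2 and 3 x ULN is thus pooled with values from 1.5 x ULN, and by itself does not reach the Grade 3 or 4 listing of SAP 7.2.2.2.

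**5. Size per subject.** One subject is 100 / N points: 5 at N = 20, 10 at N = 10, 20 at N = 5. At N = 20, the exact two-sided 95% upper limit is 1 − 0.025^(1/20) = 16.8% for 0/20, against 24.9% for 1/20. Protocol 4.1 targets about 20 subjects; SAP 1 says enrollment ended early, and the final N is not stated.

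**6. INR.** The same-date counting sentence names only bilirubin. The denominator sentence covers all relevant tests, but nothing says when ALT/AST and INR must coincide for the numerator. INR is in the coagulation panel, which is not in the minimum set for an unscheduled visit (Protocol 6.4.5).

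**The case against.** The strongest reply is that little is lost. The rule asks for both values above their limits on one date. It does not ask that they cross together, and it does not refer to the ALT/AST peak. With a shared panel and twice-weekly sampling, most overlapping elevations will be seen and counted. A non-overlapping case is still in the close-observation row and two listings, and in a study this small every liver case can be read individually. All of this stands, and it confines the point to one table row.

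Three stronger readings are tempting, and the documents do not support them:

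- A reader might infer that any bilirubin rise following the ALT/AST peak is lost. Subject A shows that it is not.
- A reader might infer that the SAP departs from the protocol, whose legible text has no same-date condition. The withholding criteria are in Figure 7-2, which is not shown, so whether it requires concurrent values cannot be checked.
- A reader might want a percentage of cases missed. Simulations with assumed peaks, half-lives and lags of 0 to 10 days give anything from 0% to 81% of subjects who cross both limits. That span reflects the assumptions. It is also in multiples of ULN, whereas subjects with elevated baseline are judged against baseline or 300 U/L.

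The same-date denominator is not a separate source of bias for the bilirubin row: the tests share a panel, and a smaller denominator would raise the percentage.

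It is also fair to say that no document favours 30 days over 7 or 14, and that a longer window admits unrelated events. Protocol 1.5 itself mentions biliary obstruction in a PSC subject. That is a reason not to replace the same-date count. It is not a reason to omit a second row. The listings hold the data, but neither is stated to pair the two dates, and 7.2.3 has no bilirubin-only row.

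**Conclusion.** The point holds in a narrow form. The composite row omits subjects whose ALT/AST and bilirubin elevations do not overlap on any sampled date. Against a windowed numerator this rule can only under-count, and no windowed count is planned. The under-count is of a tabulated composite; the underlying values remain in the listings.

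The expected number of missed subjects cannot be obtained from the documents, which give neither an event rate nor a lag. What can be said is the weight of one case: 5 percentage points at N = 20 and more with fewer subjects. The direction follows from the SAP wording alone. The persistence times rest on assumed half-lives and serve only to show that either outcome is plausible. The missing timing rule for the INR numerator is a separate, smaller gap in the same paragraph. This is a cheap improvement to reporting and does not invalidate the planned analysis.

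**What to change.** In SAP 7.2.3:

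- Keep the same-date count for ALT/AST plus bilirubin as it is.
- Add a supplementary row for subjects whose bilirubin exceeds its limit on the date of, or within a prespecified number of days after, an ALT/AST value above its limit. Thirty days is one possible choice; what matters is that the length is fixed in advance.
- Use as denominator for that row the subjects with at least one postbaseline value of each test.
- State the same timing rule for the ALT/AST-plus-INR criterion.
- Show in the listing the dates and values of both components.

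The cost is a few lines of SAP text and one programming change, with no new data. The downside is that an occasional unrelated later bilirubin rise, for example from biliary obstruction, will enter the supplementary row and must be explained in the listing. At N = 20 such a case also moves that row by 5 points, which is why it should stand beside the same-date count and not replace it. The change affects reporting only and leaves the protocol's withholding rule untouched.
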